### 4.3 Other Diagnostic Methods

Real-time quantitative Polymerase chain reaction based methods will also be used to determine the etiology of CABP at baseline.

- Frozen sputum samples will be analyzed by RQ-PCR using specific and conserved primers for the target genes based on current published studies (see [Table 1](#)). Single-plex RQ-PCR will be set up, validated and sputum samples will be analyzed by a specialized Good Laboratory Practices-certified bioanalytical laboratory (Accelero Bioanalytics GmbH, Germany).
- Oropharyngeal specimens will be analyzed by a specialized laboratory ([name], Diagnostic Mycoplasma Laboratory, UAB, AL, USA) using RQ-PCR for *Mycoplasma pneumoniae* (*repMp1*) and for detection of macrolide-resistance (23S rDNA).
- Nasopharyngeal specimens will be analyzed by a specialized laboratory ([name], Emory University, GA, USA) using RQ-PCR for detection of *S. pneumoniae* (*lytA*).

Amplified genes and cut-off values for the definition of a pathogen from the oropharyngeal and nasopharyngeal swabs are presented in [Table 1](#).

**Table 1. Amplified Genes and Cut-off Values for RQ-PCR**

Specimen / Organism	PCR	Proposed Amplified gene a	Cut-off values for consideration of the organism as definite etiological significant for CABP	
			Cut-off values	Reference
Sputum				
S. pneumoniae	RQ-PCR	lytA	DNA corresponding to $\geq 10^4$ CFU/mL	Albrich et al, 2014
H. influenzae	RQ-PCR	frdB	DNA corresponding to $\geq 10^6$ CFU/mL	Johansson et al, 2010; Kais et al, 2006
M. catarrhalis	RQ-PCR	copB	DNA corresponding to $\geq 10^6$ CFU/mL	Johansson et al, 2010; Kais et al, 2006
S. aureus	RQ-PCR	nuc	DNA corresponding to $\geq 6 \times 10^5$ CFU/mL	Huang et al, 2015
M. pneumoniae	RQ-PCR	CARDS TX gene	Positive	Thurman et al, 2011; Waites et al, 2012
L. pneumophila	RQ-PCR	ssrA	Positive	Thurman et al, 2011
C. pneumoniae	RQ-PCR	argR	Positive	Thurman et al, 2011
Oropharyngeal swabs				
M. pneumoniae	RQ-PCR	repMp1	Positive	Thurman et al, 2011; Waites et al, 2012
Nasopharyngeal swabs				
S. pneumoniae	RQ-PCR	lytA	$\geq 1 \times 10^3$ CFU/mL	Chochua et al, 2015

a RQ-PCR will amplify the proposed genes provided that the validation is successful. If the RQ-PCR for the proposed target gene cannot be validated, another gene target will be used.

## 5.0 ANALYSIS SETS

### 5.1 Intent-to-Treat (ITT) Analysis Set

The ITT Analysis Set will consist of all randomized subjects regardless of whether or not the subject received study drug. A subject is considered randomized when an IRT-generated randomization number has been assigned.

### 5.2 Modified Intent-to-Treat (mITT) Analysis Set

The mITT Analysis Set will consist of all randomized subjects who receive any amount of study drug. Subjects are analyzed based on the randomized (ie, assigned) treatment group.

### 5.3 Safety Analysis Set

The Safety Analysis Set will consist of all randomized subjects who receive any amount of study drug. Subjects are analyzed based on the study drug actually received. All safety analyses will be conducted in this population.

### 5.4 Microbiological ITT (microITT) Analysis Set

The microITT Analysis Set will consist of all subjects in the ITT Analysis Set who have at least 1 baseline bacterial pathogen known to cause CABP as defined in Sections 4.1 and 4.2. Additional isolates not a priori defined as pathogens in this SAP will be evaluated on a case by case basis by the Evaluability Review Team.

### 5.5 Microbiological ITT-2 (microITT-2) Analysis Set

The microITT-2 Analysis Set will consist of all subjects in the ITT Analysis Set who have at least 1 baseline bacterial pathogen known to cause CABP as defined in Sections 4.1 and 4.2 from a diagnostic method other than PCR. Thus, the following will *not* be considered pathogens for the microITT-2 Analysis Set:

- *Streptococcus pneumoniae* from RQ-PCR of nasopharyngeal swab
- *Streptococcus pneumoniae*, *Haemophilus influenzae*, *Staphylococcus aureus*, or *Moraxella catarrhalis* from RQ-PCR of sputum
- *Legionella pneumophila*, *Mycoplasma pneumoniae*, or *Chlamydomphila pneumoniae* from RQ-PCR of sputum
- *Mycoplasma pneumoniae* from RQ-PCR of oropharyngeal swab

### 5.6 Clinically Evaluable (CE) Analysis Sets

Three CE Analysis Sets will be defined, the CE-EOT, CE-TOC and CE-LFU Analysis Sets. The CE Analysis Sets will consist of all subjects in the ITT Analysis Set who also meet the criteria listed below. These criteria will be programmed from the electronic case report form (CRF) data and/or reviewed manually by the Sponsor in a blinded manner prior to database lock to confirm

each subject's inclusion in or exclusion from the CE Analysis Sets. Details regarding the programming and review of eCRF data are included in the Evaluability Review Plan.

1. Subjects must meet all of the inclusion criteria below to be included in the CE-EOT, CE-TOC and CE-LFU Analysis Sets.

Inclusion criterion 3: Have an acute illness ( $\leq 7$  days duration) with at least 3 of the following symptoms consistent with a lower respiratory tract infection (new or worsening):

- Dyspnea
- New or increased cough
- Purulent sputum production
- Chest pain due to pneumonia

Inclusion criterion 4: Have at least 2 of the following vital sign abnormalities:

- Fever (body temperature  $>38.0^{\circ}\text{C}$  [ $100.4^{\circ}\text{F}$ ] measured orally or equivalent temperature from alternate body site) or hypothermia (body temperature  $<35.0^{\circ}\text{C}$  [ $95.0^{\circ}\text{F}$ ] measured orally or equivalent temperature from an alternate body site)
- Hypotension (systolic blood pressure  $<90$  mmHg)
- Tachycardia (heart rate  $>100$  beats/min)
- Tachypnea (respiratory rate  $>20$  breaths/min)

Inclusion criterion 5: Have at least 1 other clinical sign or laboratory finding of CABP:

- Hypoxemia (ie,  $\text{O}_2$  saturation  $<90\%$  on room air or while receiving supplemental oxygen at subject's baseline requirement or  $\text{PaO}_2 <60$  mmHg)
- Auscultatory and/or percussion findings consistent with pneumonia (eg, crackles, egophony, dullness)
- White blood cell (WBC) count  $>10,000$  cells/ $\text{mm}^3$  or  $<4500$  cells/ $\text{mm}^3$  or  $>15\%$  immature neutrophils (bands) regardless of total WBC count

Inclusion criterion 6: Have radiographically-documented pneumonia within 48 hours before enrollment (ie, infiltrates in a lobar or multilobar distribution or diffuse opacities on chest x-ray or chest computed tomography scan consistent with acute bacterial pneumonia per the radiologists interpretation ). **NOTE:** If the imaging study is done more than 48 hours before enrollment but in the timeframe consistent with onset of the subject's symptoms, the subject will be included in the CE Analysis Sets as long as the imaging study shows an infiltrate or diffuse opacities consistent with CABP.

Inclusion criterion 7: Have a PORT Risk Class of II, III or IV and be an appropriate candidate for oral antibiotic therapy as treatment for the current episode of CABP.

2. Completed the visit within the protocol mandated window:
  - For the CE-EOT Analysis Set:
    - Completed the EOT Visit on the day of last dose of study drug or within 2 days after the last dose of study drug.
  - For the CE-TOC Analysis Set:
    - Completed the TOC Visit 5-10 days after the last dose of study drug, unless the subject was considered a failure at the EOT Visit based on the IACR.
  - For the CE-LFU Analysis Set:
    - Completed the LFU Visit Day 30 ( $\pm 3$  days) unless the subject was considered a failure at either the EOT or TOC Visit based on the IACR.
3. Must not have had a clinical response of indeterminate based on the IACR at EOT (CE-EOT Analysis Set), TOC (CE-TOC Analysis Set) or LFU (CE-LFU Analysis Set).
4. Duration of study drug was at least 48 hours, unless the subject died prior to 48 hours.
5. Did not receive another systemic antibacterial from the first dose of study drug through EOT (CE-EOT), through TOC (CE-TOC) or through LFU (CE-LFU) with likely or documented activity against confirmed or potential CABP pathogens, unless the antibacterial was administered due to clinical failure (or relapse at LFU) or the subject had been classified as clinical failure by the Investigator prior to receipt of the antibacterial. Subjects who do not have a pathogen isolated at baseline and receive a concomitant antibiotic with activity against any potential CABP pathogen will be excluded from the relevant CE-EOT, CE-TOC and CE-LFU Analysis Set(s), unless the antibacterial was administered due to clinical failure (or relapse at LFU) or the subject had been classified as clinical failure by the Investigator prior to receipt of the antibacterial.
6. Received the correct study drug, based on randomization assignment, for all active doses taken.
7. Study personnel involved in the assessment of efficacy, or monitoring of the efficacy data, remained blinded to the subject treatment assignment through EOT (CE-EOT), TOC (CE-TOC) or LFU (CE-LFU) Visits. Subjects whose treatment assignments were unblinded to study personnel due to an adverse event (AE) will be included in the CE Analysis Sets.
8. Subjects who meet any of the following exclusion criteria at baseline as indicated on the Inclusion Exclusion eCRF will be excluded from the CE Analysis Sets:

Exclusion criterion 1: Have received more than a single dose of a short-acting oral or IV antibacterial for CABP within 72 hours before randomization. **EXCEPTION:** Subjects who have received >48 hours of prior systemic antibacterial therapy for the current episode of CABP with unequivocal clinical evidence of treatment failure (ie, worsening signs and symptoms) and isolation of an organism from blood or respiratory tract that is resistant to the prior systemic antibacterial therapy provided the organism is not resistant to fluoroquinolones.

Exclusion criterion 3: Have been hospitalized for 2 or more days within 90 days prior to the onset of symptoms or have resided in a nursing home or long-term healthcare facility within 30 days prior to the onset of symptoms. **NOTE:** Residence in an independent living facility is permitted.

Exclusion criterion 4: Have confirmed or suspected CABP caused by a pathogen known to be resistant to any of the study drugs (eg, MRSA, *Pseudomonas aeruginosa*, any pathogen of the *Enterobacteriaceae* Family) or attributable to etiologies other than community-acquired bacterial pathogens (eg, ventilator-associated pneumonia, hospital-acquired bacterial pneumonia, bacterial aspiration pneumonia, *Pneumocystis jirovecii* pneumonia or other fungal pneumonia, viral or mycobacterial infection of the lung).

Exclusion criterion 5: Have a noninfectious cause of pulmonary infiltrates (eg, pulmonary embolism, chemical pneumonitis from aspiration, hypersensitivity pneumonia, congestive heart failure, bronchial obstruction, lung cancer, cystic fibrosis).

Exclusion criterion 6: Have confirmed or suspected pleural empyema (does not include sterile parapneumonic effusions).

Exclusion criterion 16: Have been previously treated with lefamulin or previously enrolled in this study.

9. Subjects who have pneumonia attributable to etiologies other than community-acquired pneumonia, a noninfectious cause of pulmonary infiltrates or confirmed pleural empyema at Screening but discovered post-baseline will be excluded from the CE Analysis Sets.
10. Any additional factor that may confound the assessment of efficacy as determined by the Sponsor during blinded review for evaluability. If a subject is excluded from the CE Analysis Sets due to an additional factor, the reason for exclusion will be documented in the appropriate analysis database and the Evaluability Review Plan.

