#### 6.8.2 Concomitant Medication

All concomitant medications taken during the study will be recorded in the subject's eCRF.

In the case that additional antibiotic treatment is required for the current episode of CABP, the subject's study drug will be discontinued and they will be considered to have an IACR of

Failure; however, subjects will continue to be followed for safety as detailed in Section 6.18.1.

Other systemic antibacterial agents that are potentially effective against pathogens associated with CABP should not be administered during the study except in the case of CABP treatment failure or when medically necessary for treatment of a concomitant infection. The following antibacterial agents are permitted:

- Anti-tuberculosis drugs isoniazid, ethambutol and pyrazinamide
- Cinoxacin
- Dapsone
- Enoxacin
- Fidaxomicin
- Methenamine Mandelate
- Metronidazole
- Naladixic Acid
- Nitrofurantoin
- Norfloxacin
- Oral Vancomycin

Although all drugs that are metabolized by CYP3A4 are not prohibited, they should only be used when necessary and with appropriate subject monitoring. *In vitro* studies demonstrated that lefamulin may inhibit the metabolism of substrates of CYP3A4; however, results obtained from Phase 1 drug interaction studies performed demonstrate that lefamulin has a marginal effect on CYP3A4 inhibition in humans and no change in lefamulin's dose is required. In addition, all drugs that are P-glycoprotein substrates are not prohibited; however, they should only be used when necessary and with appropriate subject monitoring. A list of drugs that are CYP3A4 substrates and P-glycoprotein substrates is provided in Appendix 3.

Close monitoring is recommended in subjects who require medication that can reduce potassium levels (e.g., loop and thiazide-type diuretics, laxatives and enemas [high doses], corticosteroids, amphotericin B) or medication that is associated with clinically significant bradycardia.

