#### 9.3.5 Clinically Evaluable Analysis Set

The CE Analysis Sets (CE-EOT, CE-TOC and CE-LFU Analysis Sets) will be a subset of the ITT Analysis Set that will include subjects who meet the criteria for CABP described in Inclusion Criteria Nos. 3-7, and who received at least the pre-specified minimal amount of the intended dose of study drug and duration of treatment, do not have an indeterminate response based on the IACR (at EOT for the CE-EOT Analysis Set, at TOC for the CE-TOC Analysis Set and at LFU for the CE-LFU Analysis Set), did not receive concomitant antibacterial therapy that is potentially effective against CABP pathogens (except in the case of clinical failure) from the first dose of study drug through the EOT Visit (CE-EOT Analysis Set), through the TOC Visit (CE-TOC Analysis Set) and through the LFU Visit (CE-LFU Analysis Set), and for whom there are no other confounding factors that interfere with the assessment of the outcome.

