**Table 3. Investigator’s Assessment of Clinical Response at EOT and TOC**

Outcome	EOT and TOC
Success	The subject's clinical signs and symptoms have resolved or improved such that no additional antibacterial therapy is administered for the treatment of the current episode of CABP.
Failure	A subject is a treatment failure if any of the following is met: 
 
• Signs and symptoms of CABP have not resolved, not improved or have worsened such that non-study antibacterial therapy is administered for the treatment of the current episode of CABP.
 
• Measures of inflammation such as temperature or elevated WBC have worsened or failed to improve such that non-study antibacterial therapy is administered for the treatment of the current episode of CABP.
 
• Bacteremia has worsened or failed to improve resulting in administration of non-study antibacterial therapy.
 
• The occurrence of an AE requiring discontinuation of study drug and institution of non-study antibacterial therapy for the treatment of the current episode of CABP.
 
• Death from any cause.
 

Indeterminate	Insufficient information is available to determine success or failure, specifically lost to follow-up.

For subjects who do not have an IACR of failure at the TOC Visit, a determination of clinical response (sustained success, relapse, prior failure or indeterminate) will be made at the LFU Visit as outlined in Table 4. Subjects who are deemed to have an IACR of failure at the TOC Visit will not have an IACR performed at the LFU Visit and will be considered to have an IACR of prior failure at the LFU Visit.

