## 7.6 Handling of Missing Data

For ECR, missing data will be handled as follows:

- If any component of ECR is missing in the time frame detailed in Section 6.1 (unless the subject dies or is deemed a failure prior to this time point), or if the subject does not have at least 2 symptoms of CABP at baseline, ECR will be defined as an indeterminate.
- If the time of a post-baseline assessment of CABP symptoms obtained in the window for determination of ECR is missing but the date of the ECR assessment is known, the time will be imputed to noon on the date of the CABP symptom assessment. If the time of assessment of CABP symptoms obtained on or prior to the date of the first dose of study drug is missing, the time will be imputed to 00:00.
- Missing start and stop times of antibiotics will be set to 00:00 on the start and stop date of the antibiotic.
- For the analysis of ECR in the ITT Analysis Set, where ECR may be missing (indeterminate), all subjects in the ITT Analysis Set will be included in the denominator. Thus, subjects with an indeterminate response are essentially considered as a failure.

For IACR, missing data will be handled as follows:

- A missing IACR at the EOT Visit will be considered indeterminate at the EOT Visit.
- A missing IACR at the TOC Visit will be considered indeterminate unless the IACR at the EOT Visit is failure. An IACR of failure at the EOT Visit will be carried forward to the TOC Visit.
- A missing IACR at the LFU Visit will be considered indeterminate unless the IACR at the TOC Visit is failure. An IACR of failure at the TOC Visit will be carried forward to the LFU Visit.
- For the analysis of IACR at the EOT, TOC and LFU Visits in the mITT, microITT, microITT-2 and emicroITT Analysis Sets, where Clinical Response may be missing (indeterminate), all subjects who meet the analysis set criteria will be included in the denominator.
- For the analysis of IACR at the EOT, TOC and LFU Visits in the CE and ME Analysis Sets, subjects with a missing (indeterminate) IACR will not be included in the analyses, since by definition, subjects in the CE or ME Analysis Sets cannot have a missing IACR.

For microbiological response, missing data will be handled as follows:

- If a followup specimen for culture was not obtained, microbiological response at the EOT Visit will be determined based on the IACR at the EOT Visit.

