- d: Perform End of Treatment (EOT) assessments at the study site within 1 day (up to 2 days permitted) after the last dose of study drug or at the time of premature discontinuation of study drug or early withdrawal from study. EOT assessments resulting from premature discontinuation of study drug should be done in place of the regular study visit on Days 1 to 7.
- e: Perform Test of Cure (TOC) assessments at the study site 5–10 days after the last dose of study drug. All subjects will have a TOC Visit irrespective of early clinical failure or receipt of an alternative antibiotic.
- f: Perform Late Follow Up (LFU) assessments at the study site on Day 30 ± 3 days. All subjects will have a LFU Visit irrespective of early clinical failure or receipt of an alternative antibiotic.
- g: Obtain informed consent before initiating any study-specific assessments or procedures.
- h: Assessment or procedure may occur at either Screening OR prior to the first dose of study drug on Day 1 once eligibility has been determined.
- i: All subjects will have vital signs and O2 saturation evaluated at Screening/Baseline and Day 1. If screening/baseline and Day 1 occur on the same calendar day, vital signs and O2 saturation do not need to be repeated. All subjects will also have assessments at EOT and TOC; at LFU, vital signs should be performed if medically indicated. If EOT and the last day of study drug are the same day, vital signs do not need to be repeated, they may be recorded once on that day (i.e., as part of the EOT assessment). Record the vital signs associated with the highest temperature after the first dose of study drug.  
**INPATIENTS:** Vital signs, O2 saturation, and supplemental O2 usage will be measured daily. If multiple vital signs are taken on a study day, the highest temperature and the vital signs associated with that high temperature will be recorded.  
**OUTPATIENTS:** In addition to the above time points, vital signs, O2 saturation and, if applicable, supplemental O2 usage will be measured at the study visit scheduled 96 ± 24 hours after the first dose of study drug.

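### SAP 5.6 criterion 2 drops from CE-TOC a subject who dies after EOT and before the TOC visit, although Table 3 makes that death a Failure (minor)

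*SAP*

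**What the plan says.** SAP 5.6 builds the CE sets from ITT subjects who meet every listed criterion. For CE-TOC, criterion 2 reads "Completed the TOC Visit 5-10 days after the last dose of study drug, unless the subject was considered a failure at the EOT Visit", with failure judged by the IACR. Criterion 3 removes anyone whose IACR at the visit is indeterminate. Criterion 4 (at least 48 hours of study drug) has a death exception, but only for death before 48 hours. Criterion 10, "Any additional factor that may confound the assessment of efficacy as determined by the Sponsor during blinded review for evaluability", is a further ground for exclusion.

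SAP Table 3 lists "Death from any cause" among the conditions for Failure at EOT and TOC, and protocol 6.12.1 does the same. SAP 7.6 says: "A missing IACR at the TOC Visit will be considered indeterminate unless the IACR at the EOT Visit is failure".

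Protocol 9.3.5 sets no visit-completion condition. Its only outcome-based condition is that subjects "do not have an indeterminate response based on the IACR". SAP 9.0 does not list the visit condition as a change from the protocol.

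The neighbouring bullets of criterion 2 differ. CE-EOT requires "Completed the EOT Visit on the day of last dose of study drug or within 2 days after the last dose of study drug" and has no exception. CE-LFU excepts an IACR failure at either EOT or TOC.

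Under protocol 9.6.1, the EMA conclusion needs a lower limit above -10% in both mITT and CE-TOC.

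**The concern.** The visit condition removes a subject whose outcome is known. A death between EOT and TOC is a Failure by definition, and the death is also the reason why the visit was not made. Every subject lost this way is a failure, so the rule can only raise an arm's CE-TOC success rate. ME-TOC inherits the loss because it is built from CE-TOC.

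It looks like an oversight. The SAP protects deaths in criterion 4, and its ECR definition (6.1) counts a death even when no symptom assessment was done. The CE-LFU bullet excepts a TOC failure, so if the death is classed by Table 3 the same subject could count in CE-LFU as a prior failure while missing from CE-TOC.

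At stake is one of the two sets that the EMA decision rests on, assuming that the addendum uses this CE definition.

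**Working it through.** **Who is affected.** Take a subject who is a success at EOT and dies on day 4 after the last dose.
- Criterion 2: no TOC visit and no failure at EOT, so the subject is excluded.
- Criterion 3: by Table 3 the subject is a Failure and passes. By SAP 7.6 read literally, the missing TOC IACR is Indeterminate and the subject is excluded here too. Both places therefore need the edit.
- Criteria 4 and 10: neither restores the subject.
- A death recorded as Failure at EOT is covered by the existing exception.

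**The plan's own figure.** Inputs from SAP 7.1: 738 × 0.80 = 590, so 295 per arm; success 85% in both arms; margin 10%; one-sided alpha 0.025; continuity-corrected Z with unpooled variance. Power = Φ[(0.10 − 1/n)/SE − 1.96], with SE = √(2 × 0.85 × 0.15/295) = 0.0294. This is Φ[(0.10 − 0.0034)/0.0294 − 1.96] = Φ(1.326) = 90.8%, against the stated 91%.

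**Power if these deaths are kept as failures.** The number is not in the documents; 1 to 5 per arm is an assumption. With k deaths kept, n = 295 + k and the success rate is 0.85 × 295/n. Power is 90.4% for k = 1, 90.1% for 2, 89.8% for 3 and 89.2% for 5.

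**Shift per unbalanced death.** The continuity-corrected lower limit is d − 1.96 × SE − ½(1/n₁ + 1/n₂).
- 251/295 in both arms: 0 − 1.96 × 0.02934 − 0.00339 = -6.09 points.
- One lefamulin death kept (251/296 versus 251/295): -0.29 − 5.77 − 0.34, or -6.39 before rounding of the parts. The shift is 0.30 point down.
- One moxifloxacin death kept: -5.82, a shift of 0.27 point up.

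**Near the margin** (unstratified limits, standing in for the stratified EMA method):

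| Lefamulin vs moxifloxacin | Method | Lower limit |
|---|---|---|
| 239/295 vs 251/295 (death kept) | Miettinen-Nurminen | -10.17 |
| 239/294 vs 251/295 (one lefamulin death dropped) | Miettinen-Nurminen | -9.88 |
| 239/294 vs 251/294 (one dropped per arm) | Miettinen-Nurminen | -10.16 |
| 240/295 vs 251/295 | Continuity-corrected Z | -10.09 |
| 240/294 vs 251/295 | Continuity-corrected Z | -9.80 |
| 240/294 vs 251/294 | Continuity-corrected Z | -10.07 |

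**Direction.** Suppose the true rates are 75% versus 85%, exactly at the margin, and all lost subjects are failures.
- Equal loss of 1% of each arm: 75/99 − 85/99 = 75.76% − 85.86% = -10.10 points. In simulation the false-pass rate goes from 2.5% to 2.3%, slightly conservative.
- Loss in proportion to failures, 4% of them in each arm: 75/99 − 85/99.4 = 75.76% − 85.51% = -9.75 points. The false-pass rate is 3.0%, and 3.5% if 8% of failures are lost.

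These loss fractions are assumptions. In 295 subjects, 4% of failures is about 3 lefamulin and 2 moxifloxacin deaths (295 × 0.25 × 0.04 = 2.95; 295 × 0.15 × 0.04 = 1.77).

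**The case against.** The strongest objection is size. The gap catches only a subject who was not failing at EOT and died within days. Primary ECR is unaffected, mITT counts the subject against success and must also pass for the EMA, and the rule applies to both arms under blinded review. The margin example is a knife edge: at 240/295 the Miettinen-Nurminen limit is already -9.81 and passes either way, and one death dropped per arm changes nothing. All of this stands, and it is why the point is minor.

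A second objection is that SAP 5.6 provides for manual blinded review to confirm each subject's inclusion or exclusion, with details in the Evaluability Review Plan. That plan or the EMA addendum may already keep these deaths. This stands as a limit on the practical consequence. It does not change the written criterion, which a review plan should not have to contradict.

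A reader might go further and infer that living subjects given other antibacterial therapy after EOT are lost in the same way. The documents do not support that. SAP Appendix A says "All subjects will have a TOC Visit irrespective of early clinical failure or receipt of an alternative antibiotic", so such a subject leaves CE-TOC only for a missed or late visit, just as a success would. Keeping only the failures among out-of-window subjects would make inclusion depend on outcome, and assigning Failure by program would override the Investigator. Nor does protocol 6.8.2 clearly conflict with SAP 7.6. Its statement that "study drug will be discontinued and they will be considered to have an IACR of" Failure concerns subjects still on study drug.

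**Conclusion.** The point holds on the text and is minor. As written, criterion 2 removes a known failure from CE-TOC and ME-TOC because of the failure itself, and no available passage restores it. The expected effect is small: about 0.3 point on the lower limit per unbalanced death, and under 2 points of power even if five deaths per arm are kept. It could change the CE-TOC conclusion only when the lower limit is close to -10% and the deaths are unbalanced.

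Two stronger readings are tempting. One is that the rule biases the trial toward non-inferiority. The documents give no death counts for this interval and no reason to expect more in lefamulin. Losing deaths in one arm only is arithmetic illustration, not evidence of likely size. The other is that a formal FDA test is at risk. SAP 3.0 names non-inferiority in CE-TOC as a secondary objective, but SAP 8.5.3.1 prescribes only confidence intervals, with no margin or decision rule. The formal CE-TOC rule is the EMA's.

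The conclusion assumes that the EMA addendum adopts the SAP 5.6 definition and that the Evaluability Review Plan does not already provide for these deaths.

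**What to change.** 1. In SAP 5.6 criterion 2 for CE-TOC, keep the existing exception and add: 'or died after EOT and on or before the earlier of the TOC Visit and day 10 after the last dose'. A later death with no TOC visit stays excluded as a missed visit.
2. In SAP 7.6, add that such a death is an IACR of Failure at TOC, not Indeterminate.
3. For consistency, give CE-EOT the same kind of death exception, and give CE-LFU one for a TOC success who dies before the LFU visit, which Table 4 already classes as Relapse. These analyses are descriptive (SAP 8.5.4), so this is tidying.
4. Carry the wording into the EMA addendum and check that the Evaluability Review Plan agrees.

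Do not extend the exception to non-study antibacterial therapy.

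The cost is one clause and one sentence, plus the matching edits, before database lock. No new data are needed: vital status is sought to Day 28 even after withdrawal (protocol 6.18.2), and SAEs are collected through LFU (SAP 8.7.1). CE-TOC success rates may come out slightly lower than under the current rule.
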